Effects of Blood Flow Restriction Training Combined with Abdominal draw-in Maneuver on Transverse Abdominis Strengthening

CRREC-109-007

Date: 2021/09/14

I. Study Protocol:

Healthy adults (age ranged 18-34 years and BMI between 18.5~24.99) were randomly recruited in the study. For the intervention group, an inflatable cuff (14 cm in width * 84 cm in length) is warped around abdominal muscles below ribs which may cause to at least 60% restriction of blood flow detected by Power Doppler ultrasonography. All participants are instructed to perform ADIM both condition of BFR and BFR-free twice a week, for four weeks. Core muscle thickness will be measured at rest and at draw-in by 2D ultrasound. Abdominal core stability, strength and endurance test by double leg lowering test, dynamometer and abdominal static endurance test.

II. Statistical Analysis Plan

Two-way mixed design ANOVA test is used to measure the group difference, time difference and interaction. Using Bonferroni post hoc test to analyze the difference among timepoints within group and Independent t test for the difference between two groups.

III. Results

1. Muscle thickness measured by ultrasound

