1.1 Transverse abdominis

Measured by two-way mixed design ANOVA, there is no main time effect, group effect and interaction of time and group of mean bilateral thickness of transverse abdominis (TrA) at rest. At draw-in, there is no main time effect but group effect and interaction of time and group of mean bilateral thickness of TrA. Of muscle thickness change between draw-in and resting, there are main time effect, group effect and interaction of time and group of mean bilateral thickness of TrA.

Before training, there is no significant difference between ADIM+BFR group and ADIM group of TrA thickness at rest, draw-in and thickness change(p>0.05). After 3 weeks of training, there is no significant difference between ADIM+BFR group and ADIM group of TrA thickness at rest. ADIM+BFR group shows significant thicker muscle at draw-in and thickness change. After 4 weeks of training, there is no significant difference between ADIM+BFR group and ADIM group of TrA thickness at rest. ADIM+BFR group shows significant thicker muscle at draw-in and thickness change. One week after the end of training, there is no significant difference between ADIM+BFR group and ADIM group of TrA thickness at rest. ADIM+BFR group shows significant thicker muscle at draw-in and thickness change.

ADIM+BFR group shows no significant difference of TrA thickness among timepoints at rest. There is significant increase at week 4 and one week after the

end of training compared with baseline and at week 4 compared with week 3 at draw-in. There is significant thickness change at week 3, 4 and one week after the end of training compared with baseline. There is no significant difference at rest, at draw-in and thickness change among timepoints in ADIM group.

2. Abdominal functional test

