2.2 Abdominal strength test

Measured by two-way mixed design ANOVA, there is main time effect but no group effect and interaction of time and group.

Before training, there is no significant difference between ADIM+BFR group and ADIM group of abdominal strength test measured by dynamometer, so as after 3 weeks of training. However, ADIM+BFR group shows significant increase after 4 weeks of training and one week after the end of training, which shows better core strength.

ADIM+BFR group shows significant different among timepoints. Compared with baseline, it shows significant increase after 4 weeks of training and one week after the end of training. Furthermore, after 4 weeks of training and one week after the end training, it shows significant different compared with week 3. ADIM group shows significant different after 4 weeks of training compared with baseline.

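### The visit-wise t tests ignore the pre-training value and the ANOVA group effect averages it in as an outcome, so no baseline-adjusted group difference is available at any visit

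*Combined protocol and SAP*

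**What the plan says.** The Statistical Analysis Plan (section II) is two sentences. The first sets the omnibus model: "Two-way mixed design ANOVA test is used to measure the group difference, time difference and interaction". The second sets the follow-up tests: "Using Bonferroni post hoc test to analyze the difference among timepoints within group and Independent t test for the difference between two groups". It names no covariate, no between-group test of change from baseline, and no visit contrast taken from the model.

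The Results (section III) show that each outcome was measured before training, at weeks 3 and 4, and one week after training ended. The pre-training value is tested between groups as a visit of its own, for example "Before training, there is no significant difference between ADIM+BFR group and ADIM group of TrA thickness at rest, draw-in and thickness change(p>0.05", and it is the reference for the within-group comparisons. Thickness change in section 1.1 is draw-in minus rest at the same visit, so it is not an adjustment for baseline.

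**The concern.** The Results claim benefits visit by visit. At each visit the only between-group evidence is a t test that takes no account of where the groups started. A non-significant baseline test does not replace adjustment, because in a small trial a sizeable gap can be non-significant and part of it carries into later visits.

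The ANOVA group effect has a different weakness. It includes a visit at which training cannot yet have had an effect, and so it understates what BFR added. The interaction has neither problem, but it is one overall test and not an estimate for week 3, week 4 or follow-up. What is at stake is the size of the BFR effect at each visit, with its uncertainty.

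**Working it through.** **Inputs.** The documents give no sample size, SD or baseline-to-follow-up correlation r, so there is no figure of the plan's to reproduce. Assumed throughout: r = 0.3, 0.5, 0.7, equal between all pairs of visits; SD = 1 at each visit; two-sided 5% tests; random allocation unless stated. The four visits are inferred from the Results.

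**1. Precision at one visit.** ANCOVA multiplies the variance of the group difference by 1 − r², so the standard error is multiplied by √(1 − r²):
- r = 0.3: √0.91 = 0.95
- r = 0.5: √0.75 = 0.87
- r = 0.7: √0.51 = 0.71

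Simulated week-4 power, at an assumed 20 per arm and an effect of 0.8 SD, is 69–70% for the raw t test and 72/80/92% for ANCOVA at r = 0.3/0.5/0.7.

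**2. ANOVA group effect.** It is the mean group difference over four visits.
- Effect δ at all three post-training visits: (0 + δ + δ + δ)/4 = 0.75δ. For δ = 0.8 SD this is 0.60 SD.
- Effect only at the last two visits: (0 + 0 + δ + δ)/4 = 0.50δ, or 0.40 SD.

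**3. Chance baseline imbalance.** With no training effect, a chance baseline gap g carries r × g into the expected follow-up difference. For g = 0.5 SD that is 0.15, 0.25 or 0.35 SD. The largest gap that stays non-significant is t(0.975, 2n − 2) × √(2/n):
- 10 per arm: 2.101 × 0.447 = 0.94 SD
- 20 per arm: 2.024 × 0.316 = 0.64 SD
- 30 per arm: 2.002 × 0.258 = 0.52 SD

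Over all randomisations the t test keeps its 5% error rate. Given a baseline gap at z = 1.5, which is non-significant, its conditional error rate is 1 − Φ((1.96 − 1.5r)/√(1 − r²)) + Φ((−1.96 − 1.5r)/√(1 − r²)), or 6.2%, 8.2% and 10.1%.

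**4. Illustration: draw-in thickness at week 3 (Results 1.1).** The ANOVA result is "At draw-in, there is no main time effect but group effect and interaction of time and group of mean bilateral thickness of TrA". At week 3 the between-group finding is "ADIM+BFR group shows significant thicker muscle at draw-in and thickness change". Yet the ADIM+BFR increases over baseline are listed only at week 4 and follow-up ("end of training compared with baseline and at week 4 compared with week 3 at draw-in"), and for the other group "There is no significant difference at rest, at draw-in and thickness change among timepoints in ADIM group". A baseline gap could be part of the week-3 difference.

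To size this, randomised trials were simulated with 20 per arm and true effects of 0, 0.4, 0.8 and 0.8 SD at the four visits. Trials were kept if the baseline test was non-significant, the week-3 t test was positive, week 3 versus baseline was non-significant in both groups at 0.05/6 (six pairs of visits), and the group effect and interaction were both significant. In these trials the mean baseline gap favouring BFR is about 0.03/0.17/0.30 SD, and the adjusted week-3 difference stays significant in about 93/86/77% at r = 0.3/0.5/0.7. The reported absence of a time main effect was not imposed; imposing it does not change the reading.

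**5. If allocation was not random.** With a stable baseline gap g, ANCOVA leaves (1 − r) × g. For g = 0.5 SD that is 0.35, 0.25 or 0.15 SD. In simulation at 20 per arm with no training effect, ANCOVA is falsely positive in 19/14/9% of trials and the interaction in about 5%.

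**The case against.** **The plan already has a test that uses baseline.** This is the strongest reply, and it stands. The interaction compares change between groups and is reported present for draw-in thickness, thickness change, stability and endurance. A reader might infer that baseline enters no between-group analysis, or that these four claims lack support. Neither follows. What remains is that the interaction gives no difference at a named visit.

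**Adjustment may add little power.** Setting a week-4 ANCOVA against the interaction is not like for like, since the first has one degree of freedom and the second three. An unplanned one-degree-of-freedom contrast of the post-training mean minus baseline has power of about 72/86/97% under the assumptions of step 1, with the effect equal at all three later visits. The matching comparison is ANCOVA of the three-visit mean, at 96/96/99%. So adjustment still helps, clearly at low r and little at 0.7. At a single visit the gain over the t test is small when r is near 0.3.

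**The week-3 draw-in pattern needs no baseline gap.** This is true. A 5% between-group test and a Bonferroni-corrected within-group test can disagree by themselves, and a non-significant rise is not an absence of rise. Section 1.1 also reports a week-3 rise in thickness change for ADIM+BFR. A reader might infer that the week-3 difference is a baseline artefact; the documents do not support that, and most simulated results survive adjustment.

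**The group effect is never offered as an effect size, and no numerical results are given for any analysis.** Both are fair. The 3/4 describes what that term estimates; it does not correct a published figure.

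**Conclusion.** The point holds as a matter of precision and estimation, and is worth acting on. The planned t tests leave out a baseline that was collected, the group effect is diluted to 3/4 or less of the post-training effect, and no adjusted group difference is planned at any visit. The single-visit standard error could be multiplied by 0.95, 0.87 or 0.71, depending on an assumed r. Sample size and SD are assumed as well, so the gain cannot be fixed from the documents.

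A reader might infer that the t tests are invalid or that some reported result is false. Under random allocation the t tests are valid, and nothing here shows a result to be wrong. The protocol speaks of random recruitment and does not describe allocation, so that condition is itself an assumption.

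Strength (Results 2.2) is a separate item. The text concludes in favour of ADIM+BFR from visit-wise results although "Measured by two-way mixed design ANOVA, there is main time effect but no group effect and interaction of time and group", and the ADIM group also changed at week 4. That conclusion lacks support from the omnibus tests. It is not a consequence of the missing covariate, and it is not shown to be false.

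**What to change.** - Keep the group-by-time interaction as the test of differential change. It is unaffected by a stable baseline gap, which matters if allocation was not random.
- Replace the visit-wise t tests and the group main effect, as effect estimates, with ANCOVA per visit. Alternatively, use a mixed model of the three post-training visits with group, visit, group-by-visit and the same outcome's pre-training value. For thickness change, the covariate is the pre-training draw-in minus rest value. The group-by-visit term of this model does not test change from baseline, so it does not replace the interaction.
- Report the adjusted difference with 95% CI at all three visits for every outcome, beside the planned analysis and labelled post hoc.
- Drop the baseline significance tests.
- As a separate correction, describe strength as unadjusted visit-wise differences without a group effect or interaction.

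The cost is SAP wording and a re-run on existing data; no new measurement is needed. The drawbacks are that the results are already known, that the gain is small if r is near 0.3, and that without random allocation ANCOVA leaves part of a stable baseline gap.

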2.1 Abdominal core stability

Measured by two-way mixed design ANOVA, there are main time effect, group effect and interaction of time and group.

Before training, there is no significant difference between ADIM+BFR group and ADIM group of double leg lowering test, so as after 3 weeks of training. However, ADIM+BFR group shows significant decrease in angle of double leg lowering test after 4 weeks of training and one week after the end of training, which shows better core stability.

ADIM+BFR group shows significant different among timepoints. Compared with baseline, it shows significant decrease after 3,4 weeks of training and one week after the end of training. Furthermore, after 4 weeks of training and one week after the end of training, it shows significant different compared with week 3 and week 4.

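### Section II plans single-step Bonferroni for the within-group timepoint comparisons; Holm has the same 5% familywise bound, is never less powerful, and could alter verdicts in a few reported families

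*Combined protocol and SAP*

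**What the plan says.** Section II gives three analysis steps. The model is described as "Two-way mixed design ANOVA test is used to measure the group difference, time difference and interaction". Comparisons between visits inside an arm are handled by "Using Bonferroni post hoc test to analyze the difference among timepoints within group", and comparisons between arms by "Independent t test for the difference between two groups". No alpha, family of comparisons or step-down variant is named, and no reason for Bonferroni is given. A level of 0.05 is implied only by Results 1.1, in "TrA thickness at rest, draw-in and thickness change(p>0.05".

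The Results use four visits: baseline, week 3, week 4 and one week after training. They are compared with each other as well as with baseline. For ADIM+BFR draw-in thickness, for instance, week 4 and the later visit differ "compared with baseline and at week 4 compared with week 3 at draw-in". For transverse abdominis (TrA) in the control arm, section 1.1 says "There is no significant difference at rest, at draw-in and thickness change among timepoints in ADIM group". For control-arm strength, section 2.2 says "ADIM group shows significant different after 4 weeks of training compared with baseline". For leg lowering, section 2.1 says "ADIM+BFR group shows significant different among timepoints" and lists the contrasts, but gives no within-group result for the ADIM arm.

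**The concern.** Single-step Bonferroni holds every pair to 0.0083, however many other pairs in the family have already been rejected. Holm starts at the same threshold and relaxes it after each rejection, while keeping the 5% familywise bound. Where only significance verdicts are reported and no simultaneous intervals are planned, the extra strictness buys little.

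At stake are the unlisted intermediate contrasts. The Results draw no explicit conclusion about when gains begin, but a reader will date onset from the list of significant visits. In ADIM+BFR, draw-in thickness, strength and endurance are listed as differing from baseline at week 4 and later, but not at week 3. An unlisted week 3 contrast could reflect no change, too few participants, or a p-value lying between the Bonferroni and Holm thresholds. Only the last of these is avoidable by the choice of procedure.

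**Working it through.** **Thresholds.** Four visits give 4 × 3 / 2 = 6 pairs per arm and outcome. Alpha is taken as 0.05, two-sided.

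- Bonferroni: every pair at 0.05/6 = 0.0083.
- Holm: ordered p-values against 0.05/6 = 0.0083, 0.05/5 = 0.0100, 0.05/4 = 0.0125, 0.05/3 = 0.0167, 0.05/2 = 0.025 and 0.05/1 = 0.05, stopping at the first failure.

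Two consequences follow without any data. If Bonferroni rejects nothing, the smallest p-value exceeds 0.0083 and Holm also rejects nothing. If Bonferroni rejects k pairs, Holm tests the smallest remaining p-value at a threshold no lower than 0.05/(6 − k). So Holm can alter a family only when 0 < k < 6.

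**Applied to the reported verdicts.** Six outcomes in two arms make 12 families.

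| Family | Pairs listed as significant | Next Holm threshold | Can Holm change it? |
|---|---|---|---|
| ADIM+BFR, TrA at rest | 0 | 0.0083 | No |
| ADIM+BFR, TrA draw-in | 3 | 0.05/3 = 0.0167 | Yes, including week 3 v baseline |
| ADIM+BFR, TrA thickness change | 3 (all baseline contrasts) | 0.0167 | Only pairs among later visits |
| ADIM+BFR, leg lowering | apparently 6 | none left | Apparently no |
| ADIM+BFR, strength | 4 | 0.05/2 = 0.025 | Yes, including week 3 v baseline |
| ADIM+BFR, endurance | at least 4 | at least 0.025 | Yes, including week 3 v baseline |
| ADIM, TrA at rest, draw-in, thickness change (3 families) | 0 each | 0.0083 | No |
| ADIM, leg lowering | not reported | unknown | Unknown |
| ADIM, strength | 1 | 0.05/5 = 0.0100 | Yes, but little room |
| ADIM, endurance | 3 (all baseline contrasts) | 0.0167 | Only pairs among later visits |

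Two entries depend on reading the text. The last sentence on ADIM+BFR leg lowering in section 2.1 appears to cover all three pairs among the later visits. In section 2.3, one ADIM+BFR endurance contrast with week 3 is stated twice; if the second was meant as week 4, five pairs are rejected and the remaining threshold is 0.05.

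Week 4 v week 3 in ADIM+BFR is already significant for draw-in, leg lowering, strength and endurance. Week 3 v baseline is already significant for ADIM+BFR thickness change and leg lowering, and for ADIM endurance.

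**Size, under assumed inputs.** The documents give no sample size, SD, correlation or effect, so there is no planned figure to reproduce. Assume paired t tests, equal SDs and a common correlation r between visits. For a mean change of d SDs, the SD of the difference is √(2(1 − r)) and the noncentrality is d√n / √(2(1 − r)). With n = 20, r = 0.8 and d = 0.4, this is 0.4 × √20 / 0.632 = 2.83. The two-sided 0.0083 critical value on 19 df is 2.94, so Bonferroni power is 47%.

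Holm power depends on the other five pairs and was simulated (20,000 trials per setting). Results for week 3 v baseline:

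| Course (baseline/week 3/week 4/later, in SDs) | n per arm, r | Bonferroni | Holm |
|---|---|---|---|
| 0/0.4/0.8/0.8 | 12, 0.7 | 13.3% | 16.9% |
| 0/0.4/0.8/0.8 | 20, 0.8 | 47.2% | 60.5% |
| 0/0.4/0.8/0.8 | 25, 0.8 | 61.6% | 75.7% |
| 0/0.3/0.5/0.5 | 12, 0.7 | 6.9% | 7.9% |
| 0/0.3/0.5/0.5 | 25, 0.8 | 32.6% | 39.2% |

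With a course of 0/0.2/0.4/0.4 the gain is about 0.5 to 3 points. Over a wider grid (n = 10 to 30, r = 0.5 or 0.8) it was 0.8 to 18.8 points when later effects were strong and 0.1 to 7.9 points for weaker, control-like courses. Holm never lost a Bonferroni rejection.

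**Familywise error.** With no true change at any visit, the simulated rates of the two methods are identical, about 4% to 4.6%. When week 3 is truly unchanged and later effects are real, Bonferroni gives 1.5% to 1.7% and Holm 2.5% to 5.0%. The bound is shared; the realised rate is not.

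**The case against.** Bonferroni is valid and conservative, and it gives simple simultaneous confidence intervals. Preferring Holm is a matter of efficiency, not the correction of an error. The results are already known, and moving to a procedure that can only add significant findings is a post hoc change that invites suspicion. All of that stands, and it governs how the change should be reported. The interval advantage is unused here, since no intervals are planned or shown.

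A reader might infer that Bonferroni has caused real changes to be missed, particularly gains in the control arm. The documents do not support this. Without p-values, nothing shows that any unlisted contrast lies between 0.0083 and its Holm threshold, or that it reflects a true change. The absence of any ADIM change in TrA, the muscle named in the title, cannot be an artefact of choosing Bonferroni over Holm: those three families have no rejections and stay empty under Holm. Among reported control-arm results only strength, at 0.0100 instead of 0.0083, and endurance pairs among later visits remain open.

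A reader might also take the simulated gains as estimates for this trial. They depend entirely on assumed inputs and shrink to a few points or less for small effects.

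**Conclusion.** The point holds as a modest, low-cost improvement. For the planned within-group comparisons Holm is at least as powerful as Bonferroni at the same 5% familywise bound. It could alter verdicts in six of the 12 families, with a seventh unreported. The contrasts of most interest are week 3 v baseline in ADIM+BFR draw-in, strength and endurance, where real gains may have been missed; whether they were cannot be told from the documents. The count of affected families assumes alpha of 0.05, all six pairs in each family, and reported verdicts that follow the planned Bonferroni procedure. The point says nothing about whether BFR adds to ADIM: within-group contrasts do not test that, and the between-group t tests are untouched.

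**What to change.** In Section II, replace the Bonferroni wording with Holm step-down adjustment of the six timepoint pairs within each arm and outcome, and state alpha and the family. Mark this as a change made after the results were known. In Results 1.1 and 2.1 to 2.3, report Holm-adjusted p-values for both arms and all six outcomes beside the planned Bonferroni verdicts, not in place of them, so that any verdict that differs is visible. Include the ADIM within-group result for leg lowering, which Section II plans and section 2.1 omits; that gap needs filling whichever procedure is used.

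The cost is one phrase in the plan and a re-sort of the unadjusted pairwise p-values, which the analysis must have produced although the documents do not show them. No new data are needed. Holm has no simple matching simultaneous intervals, so any intervals reported would have to be Bonferroni-adjusted or unadjusted and labelled as such.

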1.1 Transverse abdominis

Measured by two-way mixed design ANOVA, there is no main time effect, group effect and interaction of time and group of mean bilateral thickness of transverse abdominis (TrA) at rest. At draw-in, there is no main time effect but group effect and interaction of time and group of mean bilateral thickness of TrA. Of muscle thickness change between draw-in and resting, there are main time effect, group effect and interaction of time and group of mean bilateral thickness of TrA.

Before training, there is no significant difference between ADIM+BFR group and ADIM group of TrA thickness at rest, draw-in and thickness change(p>0.05). After 3 weeks of training, there is no significant difference between ADIM+BFR group and ADIM group of TrA thickness at rest. ADIM+BFR group shows significant thicker muscle at draw-in and thickness change. After 4 weeks of training, there is no significant difference between ADIM+BFR group and ADIM group of TrA thickness at rest. ADIM+BFR group shows significant thicker muscle at draw-in and thickness change. One week after the end of training, there is no significant difference between ADIM+BFR group and ADIM group of TrA thickness at rest. ADIM+BFR group shows significant thicker muscle at draw-in and thickness change.

ADIM+BFR group shows no significant difference of TrA thickness among timepoints at rest. There is significant increase at week 4 and one week after the

end of training compared with baseline and at week 4 compared with week 3 at draw-in. There is significant thickness change at week 3, 4 and one week after the end of training compared with baseline. There is no significant difference at rest, at draw-in and thickness change among timepoints in ADIM group.

2. Abdominal functional test

